Following Markov chain Monte Carlo imputation of missing IOP data, a one-sided upper 95% confidence interval for the difference between the test and control groups (i.e., test – control) in the proportion of subjects with at least one IOP measurement ≥ 30 mmHg in the study eye at any follow-up visit will be constructed using the normal approximation to test the null hypothesis for the primary safety variable that the upper confidence limit of the 95% confidence interval for the difference is ≥ 0.117 . If the upper confidence limit is less than 0.117, then the null hypothesis of inferiority will be rejected in favor of the alternative hypothesis of non-inferiority.

Following Markov chain Monte Carlo imputation of missing cell density data, a one-sided upper 95% confidence limit for the mean difference in percent ECD loss between the test and comparator OVDs will be constructed. If the upper confidence limit is less than 5%, then the null hypothesis of inferiority for the primary effectiveness variable will be rejected in favor of the alternative hypothesis of non-inferiority.

Sample Size Calculations:

Regarding the proportion of subjects who experience at least one IOP measurement ≥ 30 mmHg in the study eye at any follow-up visit, when the sample size in each group is 165 subjects, a two-group large-sample normal approximation test of proportions with a one-sided 0.050 significance level will have 95.17% power to reject the null hypothesis that the test is inferior to the control (the difference in proportions, $\pi_t - \pi_c$, is 0.117 or greater) in favor of the alternative hypothesis that the test is non-inferior to the control (the difference in proportions, $\pi_t - \pi_c$, is less than 0.117), assuming that the expected difference in proportions is 0.000 and the proportion in the standard group is 0.117.

Regarding ECD loss, when the sample size in each group is 165 subjects, a two group 0.050 one-sided t-test will have 93.90% power to reject the null hypothesis that the test is inferior to the control (the difference in means, $\mu_t - \mu_c$, is 5% or greater) in favor of the alternative hypothesis that the test is non-inferior to the control (the difference in means, $\mu_t - \mu_c$, is less than 5%), assuming that the expected difference in means is 0% and the common standard deviation is 14.2%.

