13.3 Sample Size Determination

13.3.1 Incidence of IOP ≥ 30 mmHg

Due to their comparable rheological properties, DVisc40 and VISCOAT® OVDs are expected to demonstrate similar behavior during surgical procedures.

In published studies using VISCOAT®, VISCOAT® performed without anti-IOP prophylactic treatment where the frequency of IOP spikes ≥ 30 mmHg after surgery ranged from 0.0% to 47.5%.⁶⁻²³ Based on these studies the control OVD incidence of subjects who experience at least one IOP observation ≥ 30 mmHg is estimated to be 0.117 (11.7%). A doubling of the control OVD incidence would be problematic and clinically significant, thus the non-inferiority margin will be defined as equal to the expected rate of 0.117 (11.7%).

When the sample size in each group is 165 subjects, a two-group large-sample normal approximation test of proportions with a one-sided 0.050 significance level will have 95.17% power to reject the null hypothesis that the test is inferior to the control (the difference in proportions, $\pi_t - \pi_c$, is 0.117 or greater) in favor of the alternative hypothesis that the test is non-inferior to the control (the difference in proportions, $\pi_t - \pi_c$, is less than 0.117), assuming that the expected difference in proportions is 0.000 and the proportion in the standard group is 0.117.

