13.5.1 Primary Safety Analysis

IOP will be assessed in the study eye using Goldmann tonometry at each scheduled follow-up visit and may be assessed at unscheduled visits.

Subjects with $IOP \geq 30$ mmHg at any follow-up visit ($IOP \geq 30$ mmHg at any follow-up visit, No $IOP \geq 30$ mmHg at any follow-up visit) will be summarized using categorical summary statistics for the Safety Population by actual treatment received in a table. Missing data will not be imputed for this summary table.

Missing IOP values will be imputed using Markov chain Monte Carlo (MCMC) methods. Twenty imputed datasets will be produced using a seed of 1017144149. The variables used in the imputation model will include IOP at baseline and at each of the scheduled postoperative visits. After missing data at scheduled visits has been imputed, unscheduled visit IOP values will be added to each imputed dataset.

Within each imputed dataset, subjects will be classified as belonging to one of the following groups:

- $IOP \geq 30$ mmHg at any follow-up visit
- No $IOP \geq 30$ mmHg at any follow-up visit

This classification will be based on experiencing at least one IOP measurement of 30 mmHg or more at any follow up visit over the entire course of the study. Subjects experiencing one or more IOP spikes will be counted only once.

The difference between test and control in the proportion of subjects with $IOP \geq 30$ mmHg at any follow-up visit and the asymptotic standard error will be estimated separately for each imputation.

An estimated difference between treatment groups and a two-sided asymptotic Wald 95% confidence interval around the difference will be constructed via combination of the proportion differences and standard errors from the imputations. If all the imputations result in the same estimated difference and confidence interval, then the results of a single imputation may be used.

If the upper confidence limit (equivalent to a one-sided upper 95% confidence limit) is less than 0.117 (11.7%), then the null hypothesis of inferiority will be rejected in favor of the alternative hypothesis of non-inferiority. A p-value will also be provided for this one-sided hypothesis test.

The primary safety analysis will be repeated using the Per Protocol Population as a sensitivity analysis with observed data only (i.e. without imputation).

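### The Wald interval that decides the primary safety endpoint keeps its level at the planned 11.7% spike rate but is too liberal if the control rate falls below about 5%; a margin-restricted standard error corrects this at small cost

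*Combined protocol and SAP*

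**What the plan says.** Section 13.5.1 imputes missing IOP values 20 times, estimates the difference in spike proportions and its asymptotic standard error in each dataset, and prescribes a "two-sided asymptotic Wald 95% confidence interval" for the difference, obtained by pooling these results over the imputed datasets. The decision sentence opens "If the upper confidence limit (equivalent to a one-sided upper 95% confidence limit) is less than 0.117 (11.7"%) and goes on to reject inferiority. The same section therefore describes one interval as two-sided 95% and its upper limit as a one-sided 95% limit.

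The Synopsis (Statistical Methods) instead calls for "a one-sided upper 95% confidence interval for the difference between the test and control groups", by normal approximation. Section 13.3.1 sizes the study on a "two-group large-sample normal approximation test of proportions with a one-sided 0.050 significance level will have 95.17% power", with 165 per arm, "assuming that the expected difference in proportions is 0.000 and the proportion in the standard group is 0.117". It also reports that spike rates in published VISCOAT studies "ranged from 0.0% to 47.5"%.

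The sensitivity analyses listed in section 13.5.1 (Per Protocol, best-case, worst-case, complete-case) change the data being analysed. None changes the interval method.

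**The concern.** A Wald interval estimates each arm's variance from its observed proportion. At the non-inferiority boundary with a low control rate, that estimate is often too small. An arm with no events contributes no variance at all. The upper limit then sits too low, and non-inferiority is declared more often than the stated level allows.

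The margin is an absolute 0.117 and does not shrink with the control rate. If the true control rate were 1%, the boundary of inferiority would be a test rate of 12.7%. That is where a false claim on a safety endpoint would matter most, and it is also where the Wald limit performs worst.

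**Working it through.** **Inputs.** 165 evaluable eyes per arm, margin 0.117, planned rate 0.117 in both arms and one-sided 0.05 (section 13.3.1); 184 per arm enrolled (section 13.3.3); 1:1 allocation (section 9.1.1); Wald rule (section 13.5.1).

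**Step 1: the plan's own figure.** The unpooled standard error is √(2 × 0.117 × 0.883 / 165) = 0.03539. Then 0.117 / 0.03539 = 3.306, and Φ(3.306 − 1.645) = Φ(1.661) = 95.17%. This matches the stated power, so the sample size was set on the one-sided 5% reading. With 1.960 in place of 1.645 the same formula gives 91.09%.

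**Step 2: one case by hand.** Suppose the control arm has no spikes and the test arm has 13 of 165.

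- Wald: 13/165 = 0.0788; SE = √(0.0788 × 0.9212 / 165) = 0.0210; upper limit = 0.0788 + 1.645 × 0.0210 = 0.1133. This is below 0.117, so the test passes.
- Restricted to a difference of 0.117, the fitted rates are 0.117 and 0: SE = √(0.117 × 0.883 / 165) = 0.0250; z = (0.0788 − 0.117) / 0.0250 = −1.53. This does not reach −1.645, so the test fails.

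Wald passes up to 13 test spikes and the restricted test up to 12. If the true control rate is 0%, the size is simply the binomial tail at a test rate of 0.117: P(X ≤ 13) = 7.45% for Wald and P(X ≤ 12) = 4.32% for the restricted test.

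**Step 3: exact size over the range.** All outcome pairs were enumerated from the two binomials, with test rate = control rate + 0.117. *Wald* rejects inferiority when (difference − 0.117) / SE < −z with the unrestricted SE. *FM* (Farrington-Manning) uses the SE restricted to a difference of 0.117. Complete data, 165 per arm:

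| Control rate | Wald, nominal 5% | FM, nominal 5% | Wald, nominal 2.5% | FM, nominal 2.5% |
|---|---|---|---|---|
| 0% | 7.5% | 4.3% | 4.3% | 2.3% |
| 1% | 6.9% | 4.9% | 4.1% | 2.0% |
| 2% | 6.3% | 4.8% | 3.8% | 2.2% |
| 5% | 5.7% | 4.9% | 3.0% | 2.4% |
| 11.7% | 5.2% | 4.9% | 2.6% | 2.5% |

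The nominal 2.5% columns apply if 1.960 is used, as a literal two-sided 95% interval would require. The Wald maximum at 165 per arm is 7.6% (nominal 5%, control rate 0.25%). At 184 per arm the maxima are 7.9% (nominal 5%) and 4.75% (nominal 2.5%), so full enrolment does not remove the effect. Over control rates from 0 to 47.5% at 165 per arm, FM reaches at most 5.15% and 2.62%.

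**Step 4: power at equal rates of 11.7%.** Losses are taken before rounding.

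| Level | Per arm | Wald | FM | Loss (points) |
|---|---|---|---|---|
| One-sided 5% | 165 | 95.15% | 94.63% | 0.53 |
| One-sided 5% | 184 | 96.69% | 96.30% | 0.39 |
| Two-sided 95% | 165 | 90.83% | 90.14% | 0.70 |
| Two-sided 95% | 184 | 93.72% | 92.80% | 0.93 |

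Because the outcomes are discrete, the loss does not move smoothly with sample size. For sizes between 165 and 184 it stays at or below 0.58 points on the one-sided reading but reaches 1.32 on the two-sided reading (173 per arm). At control rates of 5% or less, power exceeds 99% with either method.

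**The case against.** The strongest reply is that the problem is absent where the trial was designed to operate. At 11.7% the Wald size is 5.2%, and at a control rate of 20% the two methods agree (5.1% each). The endpoint accumulates over all visits and includes unscheduled readings, and prophylactic IOP-lowering medication is barred, so nothing in the documents points to a rate of 1% or 2%. This stands. A reader might infer that the primary safety test generally fails to control its error rate. The documents do not support that, because the low rates are only the bottom of the cited range.

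Second, a reader might infer a breach of the declared alpha on either reading of the interval. If 1.960 is used, Wald overshoots 2.5% but peaks at 4.75%, inside the one-sided 5% of the Synopsis and section 13.3.1. A breach of the declared level arises only on the one-sided reading.

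Third, the effect on any single dataset is small. With 165 per arm and control counts of 0, 2, 3, 8 or 19, the two rules differ by at most one test-arm event. This also stands.

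Fourth, it is tempting to cap the power cost at 0.7 points. That figure belongs to 165 per arm. Imputation keeps the analysed number closer to 184, where the two-sided reading costs 0.93. Miettinen-Nurminen would cost 1.30 at 165 on that reading.

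Finally, an arm with no events loses only its own variance contribution. The combined standard error is zero only when neither arm has events.

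**Conclusion.** The point holds as a refinement. The Wald rule is adequate at the planned rate and anti-conservative when the control rate is below about 5%: with 165 per arm, nominal 5% becomes 5.7% at a control rate of 5% and about 7.5% at 0%. The plan offers no alternative interval that would reveal this. The restricted standard error holds the size at or very near nominal across the cited range.

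The conclusion rests on complete data and independent binomial outcomes. Between-imputation variance was not modelled, so restored size after combining 20 imputations is expected but not shown. Which nominal level applies depends on wording in section 13.5.1 that the sponsor must settle.

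**What to change.** 1. In section 13.5.1, state one level for the decision limit, agreeing with the Synopsis and section 13.3.1, and remove the description of the same interval as both two-sided 95% and one-sided 95%.
2. In each imputed dataset, compute the difference and its Farrington-Manning variance, restricted to a difference of 0.117. Combine by Rubin's rules: total variance = mean within-imputation variance + (1 + 1/20) × between-imputation variance. Base the decision on (pooled difference − 0.117) / √(total variance).
3. Report the interval obtained by inverting that same test. A Newcombe interval does not invert it and can contradict the decision: with 184 per arm at the 2.5% level, 8 control and 19 test spikes pass Newcombe and fail Farrington-Manning. Keep the Wald interval as a supportive result.
4. Before database lock, confirm by a short simulation that the size holds after imputation, for control rates from near 0% to the planned rate.

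The cost is SAP wording, a few lines of code, the simulation, and the power loss in Step 4. Sample size, visits and data collection do not change. Section 13 leaves further analysis detail to a SAP approved before database lock, so the change can be made there.

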13.2.2 Secondary Hypotheses

The secondary null hypotheses will be eligible for rejection only if both of the primary endpoints are met. As recommended in ICH E9, the nominal alpha risk will be 0.025 for the one-sided secondary superiority hypothesis tests.

The secondary hypotheses will be tested in two sequential families, with simultaneous testing of the hypotheses in the second family.

1. Family 1: Secondary Effectiveness Hypotheses
 - a. ECD loss superiority test
2. Family 2: Secondary Safety Hypotheses
 - a. IOP spike rate superiority test
 - b. Mean change from baseline in IOP at 6 hours post-op superiority test
 - c. Mean change from baseline in IOP at 24 hours post-op superiority test

The overall type I error for the secondary endpoint hypothesis tests in Family 2 above will be controlled by application of the Holm stepwise procedure.

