13.3.3 Overall Power and Adjustment for Dropouts

Assuming independence of the primary endpoints, the overall power of the study will be $95.17\% \times 93.90\% = 89.36\%$.

To allow for a dropout rate of up to 10%, a sample size of approximately $[165/(1 - 0.1)] = 184$ subjects per arm will be targeted for enrollment. The total enrollment target therefore will be approximately 368 subjects.

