13.5.2 Primary Effectiveness Analysis

Specular microscopy of the central cornea will be completed preoperatively and at Visit 5 (90 ± 14 days postop). Images will be evaluated by a masked reading center. If multiple cell densities are obtained from the reading center for each eye visit, then the available counts will be averaged by eye and visit (Preoperative, Visit 5) to produce a single value for each eye visit.

If one or more ITT Population eyes has a missing mean ECD value either at the preoperative visit or at Visit 5 (including due to a missed visit or due to discontinuation), then the missing data will be imputed as follows. Prior to analysis, 25 imputations of missing mean densities will be produced using the Markov chain Monte Carlo method and the variables investigator, treatment, preoperative value, and postoperative value.

For each observation in the imputed datasets, the ECD loss in percent at Visit 5 will be calculated for each eye at each visit as follows:

$$\text{Loss (\%)} = \frac{\text{Preoperative Cell Density} - \text{Visit 5 Cell Density}}{\text{Preoperative Cell Density}} \times 100\%$$

The means and standard errors from the imputed datasets will be combined to produce a continuous variable summary of the ECD (cells / mm^2) at each visit (Preoperative, Visit 5) and the percent loss at Visit 5 by randomized treatment assignment for the ITT Population.

Loss (%) will be modeled as a function of the fixed class variables treatment and investigator, separately by imputation. The parameter estimates will be combined to produce a one-sided upper 95% confidence limit for the difference in percent loss between the test

and comparator OVDs and a p-value for the hypothesis test for the ITT Population. If the upper confidence limit is less than 5%, then the null hypothesis of inferiority will be rejected in favor of the alternative hypothesis of non-inferiority.

If there are no ITT Population eyes with missing ECD data, then imputation will not be performed. Instead, the available data will be analyzed and summarized as described above.

Sensitivity analyses of effectiveness will include a best-case analysis, a worst-case analysis, a tipping point analysis, and a complete case analysis (which will use only subjects who have cell density measurements at every scheduled visit), and analysis using the PP Set.

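### Section 13.5.1 calls the upper limit of a two-sided 95% interval a one-sided 95% limit, so the co-primary safety rule can be read at one-sided 0.05 or 0.025

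*Combined protocol and SAP*

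**What the plan says.** Section 13.5.1 states that "a two-sided asymptotic Wald 95% confidence interval around the difference will be constructed" by combining the estimates from the imputed datasets. The decision sentence in the same section begins "If the upper confidence limit (equivalent to a one-sided upper 95% confidence limit) is less than 0.117 (11.7", and a limit below that value leads to a claim of non-inferiority. The section adds: "A p-value will also be provided for this one-sided hypothesis test". It gives no alpha for that p-value.

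Other places that bear on the level:

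- Synopsis, Statistical Methods: the safety rule uses "a one-sided upper 95% confidence interval for the difference between the test and control groups", compared with 0.117.
- Section 13.3.1, and the same text in the synopsis: "a two-group large-sample normal approximation test of proportions with a one-sided 0.050 significance level will have 95.17% power".
- Section 13.3.3: "Assuming independence of the primary endpoints, the overall power of the study will be" 95.17% × 93.90% = 89.36%.
- Section 13.5.2, the effectiveness co-primary: the model results are combined to "produce a one-sided upper 95% confidence limit for the difference in percent loss".
- Section 13.2.2: "the nominal alpha risk will be 0.025 for the one-sided secondary superiority hypothesis tests".

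**The concern.** An analyst cannot follow both the interval instruction and the label in 13.5.1. Using the interval as instructed tests at one-sided 0.025. Using the limit as labelled, or the synopsis rule, tests at one-sided 0.05. The p-value does not settle the matter because it has no stated threshold.

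This is the pass/fail rule of a co-primary endpoint. Section 13.7.3 requires both co-primaries for success, and 13.2.2 and 13.5.3 allow the secondary superiority claims only if both are met. A result that falls between the two limits passes under the synopsis and fails under the interval in 13.5.1. Either answer could be defended from the text once the data are known.

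**Working it through.** **Inputs.** From 13.3.1: control rate 0.117, true difference 0, margin 0.117, 165 per arm, one-sided 0.05. From 13.3.2: SD 14.2%, margin 5%, one-sided 0.05, stated power 93.90%. From 13.3.3: 184 per arm enrolled at 10% dropout.

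**1. Which limit is which.** The upper limit of a two-sided 95% interval is d + 1.960 × SE, which leaves 0.025 in the upper tail. A one-sided 95% limit is d + 1.645 × SE, which leaves 0.05. The second equals the upper limit of a two-sided 90% interval.

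**2. The plan's own figures.** SE = √(2 × 0.117 × 0.883 / 165) = 0.03539, so 0.117 / SE = 3.306.

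- One-sided 0.05: Φ(3.306 − 1.645) = 0.9517, the stated 95.17%.
- ECD, noncentral t with 328 degrees of freedom: 0.9390, the stated 93.90%.
- Product: 0.9517 × 0.9390 = 0.8936, the stated 89.36%.

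**3. The same design with the interval as written.**

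- Safety power: Φ(3.306 − 1.960) = 0.9109.
- Overall, with ECD kept at one-sided 0.05: 0.9109 × 0.9390 = 0.855.
- Largest observed difference that passes at the planning SE: 0.117 − 1.645 × 0.03539 = 0.0588, against 0.117 − 1.960 × 0.03539 = 0.0476.

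If all 184 per arm are analysed and imputation variance is ignored (an assumption), SE = 0.03351 and safety power is 96.8% at one-sided 0.05 and 93.7% at 0.025.

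**4. Exact binomial enumeration of the two Wald rules, 165 per arm.**

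| Quantity | z = 1.645 | z = 1.960 |
|---|---|---|
| Power, 0.117 in both arms | 0.9515 | 0.9083 |
| Type I error, 0.234 v 0.117 | 0.0518 | 0.0262 |

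The probability that the first rule passes and the second fails is 0.0432 at a true difference of 0, the planning case. It is 0.0900 if the test device is truly 2 points worse and 0.1254 if it is 5 points worse.

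**5. An illustrative result that flips (assumed counts).** Control 19/165 = 0.1152, test 27/165 = 0.1636.

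- d = 8/165 = 0.0485; SE = √[(0.1152 × 0.8848 + 0.1636 × 0.8364) / 165] = 0.0380.
- Limit with z = 1.645: 0.1111, pass.
- Limit with z = 1.960: 0.1230, fail.
- One-sided p against the margin: 0.036, which lies between 0.025 and 0.05.

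The largest passing test count under the two rules is 24 v 22 with 15 control events, 27 v 26 with 19, and 32 v 30 with 25. In these cases the readings are one or two events apart.

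**The case against.** The strongest reply is that the intent can be recovered. The synopsis, 13.3.1 and the parenthesis in the decision sentence all give one-sided 0.05, and 95.17% reproduces at that level and not at 0.025. The 0.025 in 13.2.2 is limited to the secondary superiority tests, and 13.5.2 uses a one-sided 95% limit for the other co-primary. On this view one phrase is a drafting slip. That largely stands as a reading of intent. It does not remove the problem, because the slip is in the instruction for computing the interval and no text gives another passage precedence.

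A second reply is that the rules are nested: anything that passes at z = 1.960 also passes at z = 1.645. Even a choice made after the data are seen could therefore not exceed the error rate of the looser rule, 0.052 by exact calculation, which is about the planned 0.05. This stands. The harm is to pre-specification and, under the stricter reading, to power. It is not an inflated risk of a false claim.

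Third, the 9.0% and 12.5% disagreement rates assume a test device that is truly worse, which is not the planning case. This is fair, and 4.3% is the figure to lead with.

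Finally, the opening of Section 13 defers further detail to an SAP approved before database lock. That gives an opportunity to correct the text, but the contradiction remains in the protocol until someone does.

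**Conclusion.** The concern holds. The equivalence stated in 13.5.1 is wrong, and the section conflicts with the synopsis and 13.3.1 on the level of a co-primary test. One-sided 0.05 is probably meant. If so, the sample size and the stated power are correct. If the two-sided 95% interval is applied as written, the test is conservative, but safety power is 91.1% rather than 95.17% and overall power 85.5% rather than 89.36%.

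These figures assume 165 analysed per arm, a rate of 0.117 in both arms, independent co-primaries as in 13.3.3, and no allowance for imputation variance. The text must be corrected before unmasking because it decides whether the study succeeds.

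**What to change.** Preferred change, which agrees with the synopsis and 13.3.1: in 13.5.1, specify a two-sided asymptotic Wald 90% interval, say that its upper limit is the one-sided upper 95% limit, and say that the one-sided p-value is compared with 0.05. This costs one sentence and one stated alpha. All power figures and the 368-subject target stay as they are.

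If the sponsor does intend the 97.5% limit:

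- Delete the equivalence statement in 13.5.1 and give alpha 0.025 for the p-value.
- Change the synopsis rule to a one-sided 97.5% limit.
- Change the safety sizing text in the synopsis and 13.3.1 to one-sided 0.025.
- Restate safety power as 91.1% in the synopsis and 13.3.1, and overall power as 85.5% in the synopsis and 13.3.3.
- Say why the safety co-primary is tested at 0.025 and the effectiveness co-primary at 0.05.

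This alternative needs no extra subjects if the lower power is accepted.

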9.3.2 Intraoperative Medications

The Investigator will use their standard surgical medications. A complete list of the standard regimen of intraoperative surgical medications used will be provided to the Sponsor or its designee prior to initiation of the study. Absolutely no IOP-lowering medications may be used prophylactically. If an IOP-lowering medication is used intraoperatively (e.g., in the case of surgical complication), the medication must be recorded in the subject's source documents and on the applicable case report form(s). Use of an IOP lowering agent under these conditions is not a reason for discontinuing a subject from the study. However, such subjects are to be excluded from the Per-Protocol (PP) and Best Case analysis populations.

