9.3.4 Management of Raised IOP

Treatment for IOP < 30 mmHg should be avoided if possible unless the Investigator considers it necessary for the safety and well-being of the subject. In the case of treatment of IOP < 30 mmHg, a specific justification must be documented in the subject's source records and on the case report form. Use of an IOP lowering agent under these conditions is not a reason for discontinuing a subject from the study. However, they are to be excluded from the Per Protocol (PP) and Best Case analysis populations.

For any IOP measurement ≥ 30 mmHg at a study visit (or as determined as medically necessary by the Investigator), the Investigator should institute a treatment consisting of one or a combination of the following options:

- Aqueous fluid release through corneal incision;
- Topical eye drops (e.g., *B*-blocker, prostamide, etc.);
- Oral medication (e.g., acetazolamide).

An IOP ≥ 30 mmHg at a study visit must be rechecked in approximately one (1) hour after the initial IOP measurement.

In the event of an IOP \geq 30 mmHg or the use of an IOP lowering treatment, the Investigator should contact the Sponsor and its representative immediately.

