10.7 Other Materials

Additional materials will include:

- ETDRS light box and charts (provided by Sponsor if needed)
- Non-contact Specular Microscope (approved by or supplied by Sponsor)
Note: The Specular Microscope must be certified by the central reading center prior to study use and all users must be appropriately certified by the central reading center prior to subject imaging.
- Urine pregnancy test for all females of childbearing potential (to be supplied by the CRO)

11 Study Procedures and Evaluations

Subjects will be examined and evaluated according to [Appendix A](#). If at any time during the course of the study the subject's IOP is ≥ 30 mmHg then the subject will be requested to come in for an unscheduled study visit(s) as necessary until the IOP is < 30 mmHg. Any treatment of IOP per investigator's discretion (paracentesis, IOP lowering drugs, etc.) at any time shall be documented and the data from those subjects shall be reported and analyzed separately.

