In addition to the primary analysis, sensitivity analyses will include a best-case analysis, a worst-case analysis, and a complete case analysis (which will include only data from subjects who have IOP measurements at every scheduled follow-up visit).

Poolability of results across centers will be assessed by performing a Cochran-Mantel-Haenszel test comparing the endpoint between the treatment groups stratified by center. The p-value for the Breslow-Day test for homogeneity of odds ratios across centers will be compared to a critical value of 0.15.

The previous analyses will be completed for the following two groups, separately, without the sensitivity analyses and poolability test:

- Subjects who received IOP-reducing intervention; and
- Subjects who did not receive IOP-reducing intervention.

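### Section 13.5.1 repeats the 0.117 non-inferiority test in subjects with and without an IOP-reducing intervention, groups formed after randomization and largely by the primary safety event; the split should be descriptive

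*Combined protocol and SAP*

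**What the plan says.** Section 13.5.1 classifies each subject by whether any follow-up IOP reached 30 mmHg, and "a two-sided asymptotic Wald 95% confidence interval around the difference will be constructed via combination" of the imputations. If the upper limit "is less than 0.117 (11.7%), then the null hypothesis of inferiority will be rejected in favor of the alternative hypothesis of non-inferiority", and a one-sided p-value is given. After the sensitivity and poolability analyses the section adds: "The previous analyses will be completed for the following two groups, separately, without the sensitivity analyses and poolability test". The groups are subjects who received an IOP-reducing intervention and subjects who did not. Section 11 also says of treated subjects that "the data from those subjects shall be reported and analyzed separately".

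On who is treated, Section 9.3.4 says "Treatment for IOP < 30 mmHg should be avoided if possible". For a study-visit IOP of 30 mmHg or more, "the Investigator should institute a treatment consisting of one or a combination of the following options". Sections 9.3.1 to 9.3.3 bar prophylactic IOP lowering. Sections 9.1.1 and 11.1.2 place randomization at surgery.

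On the Per Protocol set, Section 9.3.2 says of intraoperative IOP-lowering use that "such subjects are to be excluded from the Per-Protocol (PP) and Best Case analysis populations". Section 9.3.4 says of eyes treated below 30 mmHg: "However, they are to be excluded from the Per Protocol (PP) and Best Case analysis populations". Section 13.5.7 lists disallowed concomitant treatments among the major deviations and includes IOP-lowering treatments, without an IOP threshold.

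**The concern.** The instruction removes two items and leaves the rest, so on its face the interval, the 0.117 rule and the p-value run again in each group. Group membership is not a baseline feature. It is decided after the OVD has been used, and the main route into the treated group is the event being counted. Intraoperative use and justified treatment below 30 mmHg also lead there, so the link is strong but not complete.

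Conditioning on something so close to the outcome takes events out of one group and concentrates them in the other. The randomized balance is lost in both. The untreated group can look reassuring when the test OVD causes many more spikes, and the treated group can look unfavourable when the two OVDs are identical. Section 13.3.1 regards a doubling of the control rate as clinically significant. A table reporting that the 0.117 rule was met in untreated subjects would be easy to misread as evidence against such a doubling.

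**Working it through.** **Inputs from the plan (Section 13.3.1).** 165 per arm, control rate 0.117, margin 0.117, one-sided 0.05, stated power 95.17%.

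**The plan's figure.** SE = √(2 × 0.117 × 0.883 / 165) = 0.0354. Power = Φ(0.117/0.0354 − 1.645) = Φ(1.661) = 95.17%, as stated.

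**Assumptions.** The documents give no treated shares. Let *a* be the share of spike eyes (IOP ≥ 30 mmHg) treated and *b* the share of other eyes treated, equal in both arms. The ranges are *a* = 50%, 80%, 90% and *b* = 2% to 10%. The true rates are 23.4% (test) and 11.7% (control), a doubling that puts the overall difference exactly at the margin.

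**Within-group rate, untreated.** For overall rate *p*: p(1−a) / [p(1−a) + (1−p)(1−b)].

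Example with *a* = 0.80, *b* = 0.05:
- Control: 0.0234 / (0.0234 + 0.883 × 0.95) = 0.0271.
- Test: 0.0468 / (0.0468 + 0.766 × 0.95) = 0.0604.
- Difference 0.0333, against 0.117 overall.
- Expected untreated eyes: 165 − 22.7 = 142.3 control and 165 − 37.2 = 127.8 test.
- SE = √(0.0271 × 0.9729/142.3 + 0.0604 × 0.9396/127.8) = 0.0251.
- Chance of meeting the margin ≈ Φ((0.117 − 0.0333)/0.0251 − 1.645) ≈ 95%. Simulation gives 93%.

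**Simulation** (400,000 trials per case, Wald upper limit against 0.117, true rates 23.4% and 11.7%). Section 13.5.1 builds a two-sided 95% interval but calls its upper limit a one-sided 95% limit, so both critical values are shown.

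| Set | True within-set difference | Meets margin, z = 1.645 | Meets margin, z = 1.96 |
|---|---|---|---|
| All subjects | 0.117 | 5% | 2.6% |
| Untreated, a = 50% | 0.07–0.08 | 30–38% | 21–28% |
| Untreated, a = 80% | 0.03 | 90–95% | 85–91% |
| Untreated, a = 90% | 0.02 | over 99% | over 99% |

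Ranges run over *b* from 10% to 2%.

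**Limiting case.** If exactly the spike eyes are treated (*a* = 1, *b* = 0), the treated group is 100% against 100% and the untreated group 0% against 0%. Both differences are 0 with standard error 0, so both groups meet the margin whatever the devices do.

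**Treated group, a = 90%.**
- Truly equal arms (11.7% each): the margin is met in only 24–31% of trials (z = 1.96: 16–22%).
- Under doubling: the group holds about 37–47 test and 20–32 control eyes. The margin is met in 19%, 4% and 1% of trials as *b* goes from 2% to 5% to 10%, where the true within-group differences are about 0.08, 0.14 and 0.19.

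**The case against.** **Nothing is decided on the split.** Section 13.7.3 ties success to the primary analysis populations, Section 13.5.1 attaches no claim to the two groups, and the secondary tests in Section 13.5.3 do not use them. The primary analysis counts every spike eye, treated or not. All of this stands. A reader might infer that the split weakens the trial's safety conclusion or its type I error; the documents do not support that.

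**A pass in the untreated group is not a false pass.** A reader might set 90–95% beside 5% and call it inflated error. The two figures concern different quantities. The untreated-group difference in these scenarios is about 0.02 to 0.08, below 0.117, so meeting the margin is a correct answer to a question that says nothing useful about the OVD. This also stands, and it limits the criticism to interpretation.

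**The treated shares are assumed.** True, and the result depends heavily on them: 30% at one end, over 99% at the other. The direction follows from Section 9.3.4; the size cannot be taken from the documents.

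**Section 13 defers detail to the SAP, which could label the split.** It could, but no separate SAP wording among the documents does so, and Section 13.5.1 already specifies the test.

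**Per Protocol.** A reader might infer that Section 13.5.7 removes every eye treated for a spike. The text does not support that as the natural reading. The item concerns disallowed treatments under a deviation heading, Section 9.4 defines a deviation as not following the protocol, and Section 9.3.4 itself calls for treatment at 30 mmHg or more. The express exclusions in Sections 9.3.2 and 9.3.4 cover other cases. Only the missing threshold leaves room for doubt. A knock-on effect through Best Case is weaker still: Section 13.5.1 never names that population, and its best-case analysis sits beside worst-case and complete-case, so it may be a missing-data scenario.

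**Conclusion.** The point holds as a fault of analysis labelling and interpretation. As written, Section 13.5.1 applies the 0.117 limit and p-value to two groups defined after randomization and largely by the primary event. Neither result is a randomized comparison, and neither can inform non-inferiority of the OVD.

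Under a doubled spike rate, the untreated group would meet the margin in anything from about a third of trials to nearly all, depending on the assumed treated shares and on their being equal between arms. The conclusion is the same at z = 1.645 and z = 1.96. That the comparison is uninformative needs no assumed share; it follows from Sections 9.3.4 and 13.5.1 alone. The Per Protocol wording is a minor clarification.

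**What to change.** In Section 13.5.1, keep the split but label it descriptive. By arm, give the number of subjects who received an IOP-reducing intervention, and within each group the counts, rates and timing of IOP ≥ 30 mmHg. State that no confidence limit, p-value or comparison with 0.117 will be produced. This still meets the separate reporting in Section 11; a cross-reference there is enough. The number treated per arm, out of all randomized subjects, is the more informative comparison.

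As a minor clarification, reconcile Section 13.5.7 with Sections 9.3.2 and 9.3.4 by stating, for the analysis set only, that treatment given in response to a recorded IOP ≥ 30 mmHg is not in itself a Per Protocol exclusion. This concerns who is analysed, not who is treated.

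Cost: wording only, before unmasking, with no new data and no change to clinical management. The downside is that these two groups have no formal test.
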